8.3.3 Days 21 and 28: Monitoring via video or phone call

Community patients will be monitored via video or phone call on Days 21 and 28. If feasible for hospital patients this monitoring will be performed face to face.

- Ordinal scale status assessment – As per secondary endpoint.

Those patients who have consented can enter their data [REDACTED] on the Medidata patient application 'app'.

The video (phone) calls made to the patient may be recorded for quality assurance purposes. Patients will be asked to consent to recording of their calls during the main consenting process and at the beginning of each call, the patient will be asked to verbally confirm their consent. These recordings will be emailed immediately afterwards to a secure NHS email address where they will be stored securely on the NHS server until the end of the trial. See Section 14.3.1. This is not a requirement of trial participation but a proposed way of supporting the patient's participation on the trial.

8.3.4 Days 1-28

Review of hospital and primary care records to evaluate use of any form of supplementary oxygen, CXR/ CT reports or images to assess progression or evolution of pneumonia and evidence of pulmonary thromboembolic events plus documentation of death (COVID-19 related mortality) during trial period.

Patients who are hospitalised will be followed up following discharge. The Day 28 visit can be done up to 28 days post discharge if the patient was hospitalised at the time of day 28.

8.4 Sample collection and transport

Local arrangements for collection of samples taken at home may vary depending on the trial centre and feasibility but will include home visits by the clinical research team or patients attending site, if permitted (e.g. GP 'red hub').

8.5 Escalation of patient management

Patients will be informed of [REDACTED] indications of progressive breathlessness, or other concerning symptoms (safety rule set developed by the TMG) that should

trigger immediate self-referral to seek health advice from the appropriate channels as they normally would, according to urgency e.g. GP or dialling NHS 111 or 999. Hospital patients will be monitored by the hospital clinical team and any of these events will be managed accordingly.

- As well as the safety rules being provided to the patient, these rules will also be provided to the clinical research team making the call to the patient.
- Patients will be able to self-refer as per above however in the absence of patient action in response to a threshold being met, when the clinical researcher becomes aware during the call, this will trigger the clinical researcher to remind the patient of the safety rule set and their self-referral as needed.
- Data collected from each call will be entered on the same day by the clinical researcher and therefore be available to the PIs for review on a daily basis.

Daily video call (or phone) assessments will support reinforcement and safety netting of these safety rules, allowing for self or clinical research team referral for appropriate primary care, 111 or 999 review, in accordance with local clinical pathways. These calls to the patient will follow a set script to ensure consistent data collection and will take place at a consistent time for patient convenience but also at a time which will allow sufficient time for the Principal Investigator and/or Co-Investigator to review the data and to therefore contact the patient as needed.

Any escalation of patient management, triggered by safety signals experienced by a patient, the clinical research team will also notify the Sponsor.

Patients requiring hospital admission will have clinical investigations performed in line with clinical care. Patients requiring hospital admission will continue to take camostat unless contraindicated by clinical condition or other clinical care. Patients will be provided with a trial ID card.

For dose interruption/withdrawal criteria, see Section 5.3.3.

Table 1: Schedule of Assessments

		Screening (& randomisation if eligible)	Day 1	Days 1-7	Day 7 (+/- 1 day)	Days 8-14	Day 14 (- 2 days)	Day 21	Day 28
Assessment ⁶	Testing site	Home (or at site if permitted)	Home visit	Daily video call (or phone)	Home visit (or at site if permitted)	Daily call	Home visit (or at site if permitted)	Video call (or phone)	Video call (or phone)
Blood (FBC& U&Es & other markers)							■		
Blood - PK		X							
Pregnancy test for women of childbearing potential									
Demographics		X							
▪ Height, weight									
▪ Medical history									
▪ Risk factors									
▪ COVID-19 symptoms check									
▪ COVID-age risk									
Delivery of camostat ^c				X					
Camostat administration ^E				X					
				X					
				(first dose)					
					X				
					(if patient recovered, discontinue camostat)				
Documentation of supplementary oxygen administration/ high-flow oxygen device						X			
Assessment of:		X				X		X	
▪ ordinal scale status assessment									
Call with clinical researcher				X		X		X	X

A. The intention is that home visits, by a clinical professional, occur on Days 7 and 14 to take research bloods, PK bloods and repeat swab. However, this requirement may change if patients are permitted to provide samples by visiting the site. If the Sponsor and site decide that sampling is not required, this will be communicated to the patient. The Day 7 and 14 video (phone) calls will still go ahead as planned regardless of sampling.

■

C. If randomised to the camostat arm, patients will also receive camostat tablets to last for 14 days.

D. Two readings a day.

E. Trial packs and, for those patients randomised to the treatment arm, camostat may be delivered by courier or site staff.

■

G. For community patients, home visits can be performed on site if permitted by government guidance. **For hospital based patients these assessments may be performed face to face, if feasible.**

9 RECRUITMENT

9.1 Identification of patients

The protocol is deliberately flexible so that it is suitable for several settings from which patients could be identified and recruited. These settings can include but are not limited to:

- GP practices (either as trial sites or patient identification centres texting/phoning potential patients)
- social media, traditional media, webpage, poster and leaflet advertisement
- advertisement at testing centres
- COVID hubs
- identification through other hospital departments (e.g. Emergency Department, Accident and Emergency, Oncology etc.)
- NHS Digital
- hospitalised patients who are admitted (for any reason) and subsequently test positive for COVID-19
- test and trace, or equivalent

At the time of initial regulatory submission, the approach for community/outpatient testing was, for those patients with mild symptoms, to stay at home and self-isolate, and only present to hospital/consult NHS 111 if symptoms got worse. Testing availability was also changing on a regular basis in the UK. However, testing is expected to expand rapidly and guidance for those with mild symptoms is also subject to change, especially if patients are in a high-risk group for more severe disease.

Sites with confirmed patient pathways for testing (and collection of results) and able to identify patients for out-patient support, will be selected in the first instance to support trial recruitment. In parallel, the Sponsor continues to liaise with primary care and hospital clinicians for regional variations in how patients are being tested and therefore will open further sites once there is clarity regarding the recruitment process. These sites will be submitted as a substantial amendment for appropriate regulatory approval. The Sponsor will document the patient recruitment process for each site in site management plans

Risk assessments will be performed for each site selected to ensure appropriate monitoring, training and consenting processes are in place to ensure protection of the patient's rights, safety and well-being.

As testing availability evolves across the UK, further sites will be confirmed in the primary care and hospital settings. These site management plans will be held in the TMF.

Prior to any involvement in the trial, patients who suspect they have COVID-19 should arrange COVID testing in line with government advice.

9.1.1 Testing at COVID hubs (GP practices or walk-in centres)

If the patient results confirm COVID-19 infection and they are aware of the trial, the patient can contact the clinical trial team to register their interest in participating. Alternatively, GP sites can contact patients that they know to have newly tested positive for COVID. At this point, the main patient Information Consent Document (ICD) can be emailed to the patient and the trial can be discussed with the patient with opportunity to ask questions via a video (phone) call. The patient may also undertake basic screening questions with the clinical research team.

If the patient wishes to consent to the trial, the patient will be asked to give verbal consent over the video (phone) call, with the researcher signing the consent form at that point with the patient on the call. To complete screening assessments, blood samples and assessments are required which require a face to face visit. The intention is that community research nurses or other suitably qualified medical professionals will attend to the patient in the home. Consent will be reaffirmed before any trial procedures take place and a paper version of the ICD will be signed at the earliest opportunity, by the patient which they will then keep (to avoid risk from paper copies handled by people with infection). See Section 9.2.

If eligibility is confirmed, the patient will be randomised by the clinical trial team and the patient informed of whether they are on the treatment or control arm. All randomised patients will receive a trial pack (to include diary card, Medidata patient app instructions and consent).

and for those patients on the treatment arm, camostat tablets to cover 14 days of treatment. These packs will be delivered to the patient. The clinical trial team will speak to the patient to ensure the patient is clear with the instructions on how to use the contents of the pack.

9.1.2 Emergency Departments (EDs)

A positive COVID-19 result is required for enrolment in the CRUKD/20/002 trial.

In the absence of a known positive result, a Point of Care test (e.g. Lateral Flow test) will be performed. This is standard care in some departments, but not all. If not standard care, verbal consent for screening will be required prior to performing this test. Verbal consent should be recorded in the patient's medical notes.

In the event of a positive COVID-19 result:

If routine blood samples have already been analysed during the patient's attendance in the Emergency Department (ED), the results may be used for screening purposes (any trial-specific tests that are not performed as standard may be requested following written consent); an additional research blood draw will be taken where possible as per the patient information sheet.

Patients consented in the ED and confirmed eligible will be randomised in the department and provided with the trial pack +/- camostat. Home visits and the daily phone calls will be carried out according to the protocol. This may be by the local Primary Care Clinical Research Network Nurses or other community-based team.

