4 OBJECTIVES AND ENDPOINTS

Primary Objective and Endpoint	
Objective	Endpoint
To further assess the safety and toxicity profile of camostat, to support integration into a Phase III trial.	Causality and severity of each adverse event (AE) to camostat.
Secondary Objectives and Endpoints	
Objective	Endpoint
To confirm that the PK profile aligns with the established PK profile for the active metabolite of camostat, 4-(4-guanidinobenzoyloxy) phenyl acetic acid (GBPA).	Confirm PK parameters of GBPA as assessed by population estimates from population PK analysis (popPK).
To assess the ability of camostat to reduce the requirement for COVID-19 related hospital admission in community patients with SARS-CoV-2 infection.	Rate of COVID-19 related hospital admission in community patients with SARS-CoV-2 infection.
To evaluate the requirement for supplementary oxygen (non-invasive or mechanical invasive) in patients who have received camostat as treatment for SARS-CoV-2 infection.	Supplementary oxygen-free days at 28 days (from randomisation).
To evaluate the requirement for ventilation in patients who have received camostat as treatment for SARS-CoV-2 infection.	Ventilator-free days at 28 days (from randomisation).
To evaluate efficacy of camostat by effect on COVID-19 related clinical improvement.	
Time Frame: Days 1-28
 
Time to worst point on the scale or deterioration of two points or more (from randomisation) on a 9-point category ordinal scale.
 
9-point category ordinal scale:
 
 0. Uninfected, no clinical or virological evidence of infection 1. Ambulatory, no limitation of activities 2. Ambulatory, limitation of activities 3. Hospitalised – mild disease, no oxygen therapy 4. Hospitalised – mild disease, oxygen by mask or nasal prongs 5. Hospitalised – severe disease, non-invasive ventilation or high-flow oxygen 6. Hospitalised – severe disease, intubation and mechanical ventilation 7. Hospitalised – severe disease, ventilation and additional organ support – vasopressors, renal replacement therapy (RRT), extracorporeal membrane oxygenation (ECMO) 8. Death

Research Objectives and Endpoints	
Objective	Endpoint
[REDACTED]	[REDACTED] [REDACTED] [REDACTED]
[REDACTED]	[REDACTED] [REDACTED] [REDACTED] [REDACTED] [REDACTED]
[REDACTED]	[REDACTED] [REDACTED]

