A clinical research team member will call the patient daily during this period. On Days 7 and 14, patients will be visited at home by the clinical research team, for blood draws and COVID-19 swab (or equivalent) testing. Home visits may be replaced by patient site visits (e.g. to a 'red hub') but only in accordance with government and clinical advice. If the Sponsor and site decide that sampling is not required, this will be communicated to the patient. The video (phone) calls on Days 7 and 14 will still go ahead as planned regardless of sampling. Patients will also be called weekly (Days 21 and 28) before the follow up period ends.

Patients who are in hospital for non COVID-19 related reasons may be recruited if they tested positive while in hospital. In this situation daily phone calls may be substituted by face to face visits, if feasible, by the hospital team until the patient is discharged. At that point the patient will be managed as described above. Further detail on how patients will be recruited and managed in this situation is provided in Section 9.

Adverse events (AEs) or hospital admissions related to camostat or COVID-19 will be followed up as per Section 12.0.

During the trial period (Days 1-28), patients who are hospitalised will also be followed up, up to 28 days post discharge.

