9.1.3 Acute Assessment Units (AAUs)

Patients who present to AAUs are typically referrals from GP practices. In this setting, the process will follow that of the Emergency Department setting.

9.1.4 Hospitalised patients (admitted for any reason other than COVID-19) who subsequently test positive for COVID-19

Following admission to hospital, should a patient subsequently test positive for COVID-19, hospital teams will contact the research team (if different to the hospital team) to notify them of a possible patient. The hospital / research team will inform and consent the patient as well as coordinate the screening assessments. Patients consented in this setting and confirmed eligible will be randomised in the hospital and subsequent visits can either be performed face to face, if feasible, by the research / hospital team or via video / phone calls according to the protocol. For patients recruited while in hospital, all assessments will be performed and camostat will be given by the hospital staff (if the patient is randomised to camostat) and their routine hospital care will not be affected while participating in the trial. If patients wish to do so, they can use the Medidata patient application ('app') in addition to the diary card and app instructions and consent form can be provided.

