6.9 Efficacy

To evaluate efficacy of camostat by effect on COVID-19 related clinical improvement.

Time Frame: Days 1-28

Time to worst point on the scale or deterioration of two points or more (from randomisation) on a 9-point category ordinal scale.

9-point category ordinal scale:

0. Uninfected, no clinical or virological evidence of infection
1. Ambulatory, no limitation of activities
2. Ambulatory, limitation of activities
3. Hospitalised – mild disease, no oxygen therapy
4. Hospitalised – mild disease, oxygen by mask or nasal prongs
5. Hospitalised – severe disease, non-invasive ventilation or high-flow oxygen
6. Hospitalised – severe disease, intubation and mechanical ventilation
7. Hospitalised – severe disease, ventilation and additional organ support e.g. vasopressors, renal replacement therapy (RRT), extracorporeal membrane oxygenation (ECMO)
8. Death

Table 10 Ordinal Scale.

Efficacy population

Patient Number	Randomised Arm (Treatment or Control Arm)	Day 1 Scale	Worst Point on Scale	Deteriorated by more than 2 points (yes/no)	Time to worst point (Days)

Table 11: Summary Table for Secondary Endpoint Data.

Efficacy population

	All	Treatment arm	Control arm

Number of community patients admitted to hospital due to COVID-19			
Total number of patients			
Proportion of patients per arm			
Supplementary oxygen-free days at 28 days			
Number of patients			
Proportion of patients per arm			
Ventilator-free days at 28 days			
Number of patients			
Proportion of patients per arm			

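### Emergency Department and Acute Assessment Unit patients are randomised in the department without the admit-or-discharge decision having to be recorded first, so a COVID-19 admission from the same attendance can enter the secondary admission endpoint and can be decided by staff who may know the arm.

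*Protocol*

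**What the plan says.** Protocol 9.1.2 (Emergency Departments): "Patients consented in the ED and confirmed eligible will be randomised in the department and provided with the trial pack +/- camostat". It then adds that "Home visits and the daily phone calls will be carried out according to the protocol". For Acute Assessment Units, 9.1.3 says: "In this setting, the process will follow that of the Emergency Department setting".

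Patients already in hospital are handled separately. The heading of 9.1.4 covers "Hospitalised patients (admitted for any reason other than COVID-19) who subsequently test positive for COVID-19", and 5.1 agrees: "Patients who are in hospital for non COVID-19 related reasons may be recruited if they tested positive while in hospital". The list in 9.1 is wider: "hospitalised patients who are admitted (for any reason) and subsequently test positive for COVID-19".

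The endpoint in Protocol Section 4 is "Rate of COVID-19 related hospital admission in community patients with SARS-CoV-2 infection". Table 11 (SAP document, 6.9) reports it as "Number of community patients admitted to hospital due to COVID-19" in the efficacy population, and 7.4 gives the window as Days 1-28. Neither document defines a community patient.

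The efficacy population (Protocol 13.1; SAP document 5.1 and 11.1) takes a camostat patient only after at least five days of drug. It takes a control patient who reaches Day 14 or who leaves earlier because of an endpoint, with hospitalisation as the example. SAP 11.1 adds an intention-to-treat analysis of this outcome only if the data permit.

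The trial is open label. Under Protocol 5.3.1, site staff randomise, the allocation goes to the Investigator, the site trial team and the Sponsor, and the patient is told.

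**The concern.** In an ED or AAU, whether to admit is often the open question of the visit. If randomisation can precede that decision, an admission minutes or hours later is an event that camostat had no time to prevent. It still looks like an outcome of the randomised comparison.

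Three things could follow:

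- **Dilution.** Events that the drug cannot affect are added to both arms.
- **Decision bias.** If those deciding on admission know the arm, a treated patient might be sent home more readily than a control, or kept in for observation. The direction is not predictable.
- **Unequal counting.** A control admitted from that attendance qualifies for Table 11 because of the admission. A camostat patient admitted in the same way qualifies only if five days of drug are received.

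The comparison is descriptive, but Protocol 13.1 says that differences between arms are there to inform future trials. It also allows a review of available clinical data that could recommend stopping accrual for efficacy or futility.

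**Working it through.** **Is there an ordering rule?** The inclusion and exclusion criteria (Protocol 6.1, 6.2) do not mention a disposition decision. Sections 9.1 to 9.1.4 do not order it relative to randomisation. Table 11 and SAP 7.4 have no exclusion for the attendance at which the patient was randomised. ED recruits receive the trial pack at once and then community follow-up, whereas in-patients receive the pack only on discharge (5.3.1). Reading ED/AAU recruits as community patients is therefore natural, though not stated.

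**The plan's own figure.** The plan gives no precision for the admission endpoint. Its only computed figure is the recruitment rate in 13.2, which reproduces with 200 approached: SE = √(0.5 × 0.5 / 200) = 3.5%, 95% CI 43% to 57%. This point does not depend on it.

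**Inputs.** From the documents: up to 50 per arm, 1:1, and absolute difference with SE for binary outcomes (13.1). Assumed, because the documents give no figures: ED/AAU share e = 10-50% of recruits; same-attendance admission a = 10-30% of those; later admission r = 10% control, 5% camostat.

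**(a) Number of same-attendance events.** i = e × a runs from 0.10 × 0.10 = 0.01 to 0.50 × 0.30 = 0.15. Per arm of 50 that is 0.5 to 7.5 patients.

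**(b) Dilution, if counted equally in both arms.** Observed risk = i + (1 − i) × r. SE = √[p₁(1 − p₁)/50 + p₂(1 − p₂)/50].

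| i | Control | Camostat | Difference (points) | SE (points) | Risk ratio |
|---|---|---|---|---|---|
| 0 | 10.0% | 5.0% | 5.00 | 5.2 | 0.50 |
| 0.01 | 10.9% | 5.95% | 4.95 | 5.5 | 0.55 |
| 0.03 | 12.7% | 7.85% | 4.85 | 6.1 | 0.62 |
| 0.09 | 18.1% | 13.55% | 4.55 | 7.3 | 0.75 |
| 0.15 | 23.5% | 19.25% | 4.25 | 8.2 | 0.82 |

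**(c) Decision bias with an inert drug** (r = 10% in both arms). If 10 percentage points fewer camostat ED/AAU patients are admitted at the index attendance, the false difference is e × 0.10 × (1 − 0.10):

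- e = 10%: 0.9 points
- e = 30%: 2.7 points
- e = 50%: 4.5 points

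One patient in 50 is 2 points.

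**(d) Unequal entry to Table 11 with an inert drug.** In the extreme case every same-attendance camostat admission stops drug before five days and leaves the table, while the admitted controls stay. The false difference is then i × (1 − 0.10), or 0.9 points (i = 0.01) to 13.5 points (i = 0.15). This is an upper bound, because Protocol 5.3.5 has admitted patients continue camostat unless contraindicated.

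**The case against.** The text leans towards discharge. ED recruits are given a pack and then home visits and calls. Section 9.1 first selects sites able to identify patients for out-patient support, and it places each site's recruitment process in site management plans. Those plans are not available and may set the order. This stands as context, but an implied sequence is not a protocol rule.

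A reader might infer that the admission decision is in fact made by staff who know the arm. The documents do not show that. They say who receives the allocation but not who decides on ED/AAU admission, and 9.1.4 allows for a research team separate from the hospital team. Only the possibility is supported.

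A reader might also infer that every same-attendance admission enters Table 11. It does not: a camostat patient with under five days of drug is outside that population, and the definition of community patient is left open.

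The move in risk ratio from 0.50 to as much as 0.82 looks large. On the absolute scale that the plan reports, dilution is at most 0.75 points (5.00 − 4.25), well within one standard error. The 10-point shift in (c) has no basis in the documents. With a = 10% it would mean abolishing every such admission in one arm.

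Finally, admission is a secondary endpoint without significance testing. Nor is it supported to say that the primary safety outcome is undermined. An admission of over 24 hours is an SAE, but COVID-19 related events are recorded and tabulated as such (SAP document 6.7), so these can be identified.

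**Conclusion.** The gap is real and its consequence is conditional. As written, the plan allows ED and AAU patients to be randomised before disposition is decided, and it allows a COVID-19 admission from that attendance to count in the admission endpoint. Dilution alone is small in absolute terms. The larger risks are a shift by arm-aware staff (0.9 to 4.5 points, against an assumed true effect of 5) and the unequal entry rule of the efficacy population, for which ITT is only a conditional safeguard. All sizes rest on the assumed ED/AAU share and admission rates. If few patients come by this route, or if site plans already put discharge first, the effect is slight. Because the endpoint is secondary and descriptive, this is an inexpensive improvement that should be made. It is not a defect that invalidates the trial.

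**What to change.** 1. In Protocol 9.1.2 and 9.1.3, state that randomisation follows the recorded admit-or-discharge decision.
2. Reconcile 9.1 (admission for any reason) with 5.1 and 9.1.4 (reasons other than COVID-19), so that it is clear whether patients being admitted for COVID-19 may enter. State whether ED/AAU recruits are community patients for the endpoint.
3. For patients already randomised, flag by date and time any admission arising from the attendance at which they were randomised.
4. Report the admission endpoint with and without flagged admissions, in all randomised community patients (ITT) as well as in the efficacy population, by one rule applied to both arms. Make the ITT version firm for this endpoint. Reporting both ways shows how much the result depends on these admissions. It cannot undo a shift already caused by knowledge of the arm; only the ordering in step 1 prevents that.

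Cost: protocol wording, one derived flag and a few extra table rows. Randomisation in the ED/AAU is slightly delayed, and a few recruits may be lost.
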